4.3 Subject Accounting and Withdrawals

A detailed summary of subject accounting over the course of the study will be prepared for each treatment group (Appendix B, Table 3 & 4). A study flow diagram, derived from the one recommended by CONSORT, will also be provided (Appendix B, Figure 1). Withdrawal rates over time and reasons for withdrawal will be summarized. For the follow-up evaluation at 22-26 month corrected GA, withdrawal rates will be compared between arms using standard methods for dichotomous measures.

4.4 Evaluation of Safety

In addition to the standard reports, statistical analyses will be performed to compare adverse event rates between treatments. In particular, the rate of pneumothorax, pulmonary interstitial emphysema (PIE), and/or other serious adverse events (that have been adjudicated as potentially relating to the intervention; see Protocol section 8.2.2). In order to minimize the risk, this safety outcome will be compared between treatment arms after 1/6 (100 subjects) have completed the primary outcome, as well as at the two planned interim analyses for the primary outcome (1/3 and 2/3), since we would not expect any statistically significant differences in the rate after 100 subjects (with O'Brien-Fleming alpha 0.000002). Instead, we will look for a clinically meaningful double the risk in the intervention versus standard care arms. (Appendix B, Table 5)

All other adverse events not explicitly mentioned in the Protocol will also be included, regardless of their presumed relationship to the study intervention. Adverse events will be collapsed into groups based on body part depending on numbers seen. The proportion of subjects

with any adverse event will be compared between groups using an exact Mantel-Haenszel test. Comparisons between interventions will be primarily descriptive

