4.6. Random Allocation in the Delivery Room

Following informed consent, the mechanics of the randomization maneuver in the DR addresses the following aspects:

- Twins and multiples will be randomized as a unit, using a single envelope.
- Envelopes will be kept immediately outside the DR, at a safe designated site suitable for each site.

There will be between 3-5 envelopes for each of the gestational age strata in each location. This will ensure that in the hurry around a pending delivery there is no excess fumbling. Selection will be sequential and the lowest number marked on the envelope will be taken.

The next numbered envelope will be taken into the DR by the NICU-DR team. Opening of the envelope, and thus randomization, will only be performed when the infant has been delivered and deemed to require respiratory assistance. Within 15-30 seconds the assessment of whether or not the baby is eligible to be randomized is possible to make in a safe manner.

We have undertaken extensive simulation of this procedure and it does not introduce time-delays. We provide here a video clip showing this procedure in action at one of these simulations on the SAIL Trial website. Our procedure is modeled on those undertaken during the pivotal COIN trial where a member of our Steering Committee ([name] Melbourne) was a co-investigator. In addition [name] was one of the site investigators for the COIN trial at McMaster University, Canada, where the process of randomization also did not impede safe practices in the DR.

Thus opening of the envelope will not impede appropriate delivery of care. All opened envelopes and assignments will be kept in the logs of the site. The research study coordinator will be available as a back-up for the clinical Neonatal DR delivery team.

5. Study Data

The following is a table of details that will be collected, and it is itemized by day of collection. It should be noted that only the details of the sustained inflation maneuver itself, and the screening log for eligible patients, is unique to this study. All other data points are routinely measured. There are no blood tests or data being collected that are not already routine clinical data.

Data Collection Topic	Specific Data Elements	Specific time interval

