6.1. Statistical Plan

6.1.1. Sample Size Determination

Sample size is based on a possible reduction in risk of neonatal mortality/BDP in infants at 36 weeks PMA receiving the SI intervention compared to those who receive the standard PEEP/CPAP. The significance level was set at $\alpha=0.038$ (due to the interim analyses), and power at 80%. Based on information from the recent multi-center NICHD SUPPORT trial² and the COIN trial,²⁰ we estimate that the baseline rate of neonatal mortality/BDP in the standard or care (control) arm by 36 weeks is 65%.

In order to detect an absolute risk reduction of 12.5%, 263 subjects per treatment arm are required. We anticipate virtually no loss to follow-up for the primary endpoint as infants will likely still be hospitalized because of their condition, will be under constant and continuing medical care. We have inflated the estimate by 1.12 to allow for twins and multiples to be randomized together. With this inflation in mind, the target sample size for this study is 300 subjects per arm.

For the secondary outcomes available in all subjects, with 263 subjects per arm (ignoring the twin correction factor), there will be 80% power to detect a difference of 0.24 standard deviation units in continuous outcomes, and a hazard ratio of 0.77 in survival outcomes under a proportional hazards assumption. Some secondary outcomes will not be available due to death of the infant, or loss to follow-up after discharge from the NICU. Overestimating these rates at 50%, we assume 130 subjects per arm will be available for the longer term secondary outcomes. With this sample size we will still have sufficient power to detect a clinically meaningful difference of at least 17% in event rates (or odds ratio of at least 2.0).

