5.4.2 Secondary Endpoints

Secondary outcomes will be analyzed using similar procedures to the primary outcome. Descriptive statistics for secondary outcome measures will be calculated. Outcomes will be compared between treatment groups using GEE methods (where needed to account for twins) with logistic regression (dichotomous outcomes), linear regression (continuous outcomes), or survival analysis (survival time outcomes), as appropriate. If indicated, these models will be expanded to include baseline covariates and potential interactions between baseline factors and intervention.

Standard data and regression diagnostics will be used to assess model adequacy and examine potential outlying or influential data points for all of the above analyses. If these analyses suggest significant skewness or other violations of parametric model assumptions, the comparisons above may be supplemented with non-parametric methods based on rank scores within the generalized Mantel-Haenszel testing framework, adjusting for clustering of multiple births.

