6. INTENT-TO-TREAT ANALYSIS AND MISSING DATA

6.1 Treatment and Study Withdrawals

It is anticipated that there will be a small number of infants who, because of acute clinical deterioration are treated according to the preference of their medical team rather than by study protocol. However, their outcomes will be measured and analyzed according to original allocation by intention-to-treat principles.

It should be noted that infants who discontinue in the trial, particularly in the case of an adverse event, will not be considered withdrawals from the study unless their parent withdraws consent for further follow-up. The parents of such infants will be encouraged to continue in the study in order to provide complete follow-up information. The characteristics at time of randomization for those participants without complete follow-up will be examined; however, there will be limited statistical power to detect any but major differences between these infants and those with complete follow-up. As mentioned above, in order to assess the potential biases introduced by differential withdrawal among intervention arms, a comparison of withdrawal rates will be carried out using the exact conditional test (ECT) version of Mantel-Haenszel methods to adjust for within-center clustering.

Potential effects of withdrawals and other sources of missing data on the statistical analysis and interpretation of results are discussed further below.

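### The any-adverse-event and withdrawal comparisons use exact Mantel-Haenszel methods that treat siblings as independent although multiples are randomised together; the error is real but small, and a delivery-clustered analysis removes it

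*SAP*

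**What the plan says.** - **Unit of randomisation.** Protocol 4.6: "Twins and multiples will be randomized as a unit, using a single envelope". Protocol 6.1.1 carries this into the sample size: "We have inflated the estimate by 1.12 to allow for twins and multiples to be randomized together".
- **Efficacy analyses.** SAP 4 compares death/BPD at the interim looks by GEE because of multiple births, and SAP 5.4.1 uses GEE for the adjusted primary analyses. SAP 5.4.2 compares secondary outcomes by "GEE methods (where needed to account for twins"), and its rank-based Mantel-Haenszel fallback is also to be adjusted for multiple births.
- **Adverse events.** SAP 4.4 has the proportion of subjects with any adverse event "compared between groups using an exact Mantel-Haenszel test". It names no strata and no sibling adjustment. SAP 5.3 carries the same method into the final report.
- **Withdrawals.** SAP 6.1 names the "exact conditional test (ECT) version of Mantel-Haenszel methods to adjust for within-center clustering". Siblings are not mentioned.
- **Status of the safety comparisons.** SAP 4.4 adds: "Comparisons between interventions will be primarily descriptive". For pneumothorax, PIE and adjudicated related events it says: "Instead, we will look for a clinically meaningful double the risk in the intervention versus standard care arms".

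**The concern.** An exact conditional test keeps its nominal level only if the infants are independent given the strata. Here siblings always fall in the same arm and share a mother, a pregnancy and a delivery. Stratifying by site, or by site and gestational age, leaves whole sibling sets inside one stratum and one arm, so it cannot remove their correlation. With positive correlation the effective number of infants is smaller than the test assumes, and the p-value is smaller than one that respects the design.

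The SAP recognises this for efficacy, and even for its own Mantel-Haenszel fallback in 5.4.2, but not in 4.4 or 6.1. Air leak, pneumothorax and the FiO₂ ≥ 40% endpoint appear both among the secondary efficacy endpoints (SAP 2.3.2) and in the safety material. The same data could therefore enter clustered and unclustered comparisons in one report. At stake is the consistency and stated error rate of p-values given to the DSMC and carried into the final report.

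**Working it through.** **1. Reproduce the plan's sample size.** Inputs from Protocol 6.1.1: control rate 65%, reduction 12.5 points (so 52.5%), α = 0.038, power 80%. SAP 5 makes tests two-sided. With pooled variance and no continuity correction, the mean rate is 0.5875:

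n = [2.075·√(2·0.5875·0.4125) + 0.842·√(0.65·0.35 + 0.525·0.475)]² / 0.125² ≈ 263 per arm, as stated.

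263 × 1.12 = 294.6, which the plan takes to 300. So 1.12 acts as a design effect (DE) for multiples on death/BPD.

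**2. Large-sample effect of ignoring siblings.** True size = 2·[1 − Φ(z/√DE)].

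- DE = 1.12: √1.12 = 1.058 and 1.96/1.058 = 1.852, so the size is 0.064 at nominal 0.05.
- On the p-value scale, a naive 0.050 becomes about 0.064, and a naive 0.010 becomes about 0.015.
- The DE for adverse events is not in the documents. Over an assumed range of 1.02 to 1.25, the size at nominal 0.05 runs from 0.052 to 0.080.

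**3. The exact test itself.** Step 2 is a normal-theory result, while the SAP names an exact test, which is conservative because its distribution is discrete. The exact conditional stratified 2×2 test was therefore simulated under no treatment effect, with siblings sharing an arm. SAP 4.4 names no strata, so both a single stratum (10,000 runs) and 21 site strata (4,000 runs; 21 sites from the Protocol Summary) were used. Event rates were 5%, 10%, 30%, 60% and 80%.

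The share f of infants in twin pairs and the intraclass correlation (ICC) are assumptions. Triplets are ignored. For twins, DE = 1 + f·ICC.

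| f | ICC | DE | Size, N = 200 | Size, N = 600 |
|---|---|---|---|---|
| 0 | 0 | 1.00 | 0.019-0.045 | 0.032-0.046 |
| 0.20 | 0.3 | 1.06 | 0.032-0.050 | 0.043-0.053 |
| 0.20 | 0.6 | 1.12 | 0.036-0.056 | 0.051-0.061 |
| 0.25 | 0.5 | 1.125 | 0.039-0.059 | 0.049-0.062 |

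Ranges run over event rates and both stratifications. The Monte Carlo standard error near 0.05 is √(0.05·0.95/10,000) ≈ 0.002 with one stratum and √(0.05·0.95/4,000) ≈ 0.003 with 21.

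**4. Reading the table.** Clustering pushes the size up. Without it, every simulated value is below 5%. At DE = 1.12 and N = 600, every value is slightly above 5%. At N = 200, the conservatism of the exact test absorbs most or all of the inflation.

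**The case against.** The case for leaving the plan alone has real weight.

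- **Scope.** A reader might infer that all adverse-event rates are tested this way. SAP 4.4 names the test only for any adverse event. Death/BPD, the primary safety endpoint, is compared by GEE at the interims, and pneumothorax, air leak and FiO₂ ≥ 40% fall under the GEE rule as secondary endpoints. This stands, with a limit: death within 48 hours and grade 3 or 4 IVH are in the safety list (SAP 2.3.3) but are not numbered endpoints in SAP 2.3.2. Table 5 of SAP Appendix B prints a p-value for each without naming a test.
- **Use.** The comparisons are mainly descriptive, and the stated criterion is a ratio of risks, which the choice of test does not change. No rule in the documents acts on the any-adverse-event p-value. This stands.
- **Size.** A reader might infer that the planned test has a 6.4% error. That is a large-sample figure with a factor borrowed from death/BPD; the simulated exact test is lower. A reader might also infer confidence intervals 5.5% too narrow (1 − 1/√1.12 = 0.055), but SAP 4.4 plans no intervals.
- **Ceiling.** Protocol 9.2.1 expects every infant to have adverse events. If nearly all do, the exact test becomes still more conservative. Rates above 80% were not simulated.
- **Withdrawals.** SAP 4.3 asks only for standard methods for dichotomous measures at the 22-26 month follow-up, which does not exclude a clustered model. The point therefore rests on SAP 6.1 alone.
- **Feasibility.** GEE can be unstable with few events. This stands, and it is why the remedy needs a second method.

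These points limit the size of the problem. They do not restore the independence that the named test needs.

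**Conclusion.** The point holds as a small error in the stated method. In SAP 4.4 and 6.1 the named exact methods assume independent infants, the design makes siblings share an arm, and the rest of the SAP allows for this. If siblings' events are positively correlated, the p-values are smaller than properly adjusted ones and the exact test's level is no longer guaranteed.

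Under a design effect of 1.12, the true size at nominal 5% is about 5-6% at the final 600 infants and 3.6-5.6% at the 200-infant look. Both ranges rest on an assumed 20% of infants in twin pairs and an ICC of 0.6, neither of which is in the documents. With weaker sibling correlation the size can stay at or below 5%. The documents therefore do not support the unconditional reading that the trial's safety p-values are too small. The consequence for decisions is small.

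**What to change.** - **SAP 4.4 (and, through it, 5.3):** replace the exact Mantel-Haenszel test with the GEE logistic model clustered on delivery, as used elsewhere in the SAP. State that the same model applies to the event-specific p-values in Table 5.
- **SAP 6.1:** use the same delivery-clustered model for withdrawals, keeping the adjustment for centre.
- **Sparse events:** use a permutation test that re-randomises whole deliveries within the randomisation strata (site by the two gestational-age groups, Protocol 4.4.4). This respects the actual unit of randomisation. Fix the rule for switching from GEE in advance.
- **At the least,** if the test is kept, name its strata and label the p-values as descriptive and not adjusted for multiples.

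No new data are needed beyond a delivery identifier, which the planned GEE analyses already require. The cost is a short edit in two sections, some programming for the permutation test, and slightly larger p-values.

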5. FINAL DATA ANALYSIS UPON COMPLETION OF TRIAL

Upon completion of the primary outcome at 36 weeks PMA, after all data has been entered in the database and query resolution is complete, the primary statistical analysis and description of the data will be performed. The final analysis for the 22-26 month cGA secondary outcomes will be completed separately, after that data has been entered in the database and cleaned. The staff biostatistician under the direction of the faculty biostatisticians will produce a final report outlining all analyses and interpretation of the results. This report will be used as the basis of the primary manuscript to be prepared for publication. Details of the analyses and statistical methods to be included in the final report are outlined below. All statistical tests described below will be conducted using a two-sided level of significance.

5.1 Examination of Baseline Characteristics

These will be reported as described above under the interim analysis.

5.2 Subject Accounting and Withdrawal Rates

These will be reported as described above under the interim analysis.

5.3 Analysis of Safety and Toxicity

These will be reported as described above under the interim analysis.

5.4 Analysis of Efficacy Endpoints

5.4.1 Primary Endpoint

In addition to the two-sample comparison (Appendix B, Table 5), adjusted analyses of the primary endpoint (death/BPD rate) may be performed. These adjusted analyses of the primary endpoint will rely on logistic regression and generalized estimating equation (GEE, to control for clustering within multiple births) methods to evaluate whether observed differences, if any, are attributable to imbalances in prognostic factors such as gender, gestational age, initial heart rate, maternal corticosteriods use, and small for gestational age (SGA). Standard regression diagnostics will be used to assess model adequacy and examine potential outlying or influential data points for these analyses. If there are clinical or demographic characteristic imbalances between the two treatment arms, a propensity score analysis (via stratification into 5 subgroups, and via inverse propensity treatment weights) will be used to assess the sensitivity of the results to any treatment allocation biases.

Prior studies offer no basis for assuming a priori interactions between treatment arms and subgroups defined by sex, race/ethnicity, gestational age, site or a combination of these groups, beyond that already controlled for in the randomization. For that reason, preplanned tests for interactions with treatment assignment are not warranted, and not powered for. We propose, however, to table all results by subgroups for descriptive purposes and to explore in secondary analyses possible subgroup differences by treatment group, solely for purposes of generating hypotheses for future studies. In particular, there is interest in exploring subgroups defined by:

- Consenting procedure which may vary by site (antenatal vs. deferred consent). While consenting procedure differences may result in some selection bias, this will be implicity adjusted for with the already planned clinical site stratification factor. Additionally, the sample size still results in 80% power at α=0.038 for the primary outcome even if the selection bias results in a reduced control arm rate.
- Route of treatment (facemask vs. nasopharyngeal tube). While not expected to modify the intervention effectiveness, exploring this difference will be important for future study design and clinical practice.
- Enrollment date. Clinical practices unrelated to this intervention, as well as increased intervention experience, could result in changes in the clinical effectiveness of the intervention over time (positively or negatively). We will explore graphically any temporal trends in the intervention effect, and will allow/test for a time-varying treatment effect via a functional logistic regression model, if needed (for which the original power calculations are conservative) ([name] SJ, et al., 2002).

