We have chosen to stratify the randomization scheme by clinical site, and gestational age (two strata 23 & 24 weeks versus 25 & 26 weeks). Stratifying on any more variables (such as gender) is not feasible with the potentially small enrollment numbers expected at some sites. We will perform a planned adjustment following the end of the trial to adjust for gender. Use of separate randomization schedules by site (ie stratified by centre, with each site having the same allocation ratio of treatment groups) ensures comparability of the treatment groups with regard to the patient mix coming from the various sites in the trial. This assurance is important because the populations can differ widely with regard to subject characteristics. Further, there may be subtle differences in the standard of care from site to site, despite the fact that this study has a well-defined plan and strict inclusion and exclusion criteria. Finally, stratification by gestational age is needed, as it is well known that mortality outcomes improve as the gestational age increases.

While there are clearly subject-specific variables that will be observed and recorded before randomization that could be used for stratification, such as gender, there are a number of problems with including more stratification variables. Of most concern, stratification by multiple variables would likely result in small numbers per group and a fairly large chance of departure from the desired allocation ratio. Since we are proposing a study with 300 subjects per group, the groups should be large enough that stratification should not be necessary to assure that the two arms will have approximately equal representation of the major confounding variables. However, a careful post-hoc analysis will be carried out to assure that the allocation was, in fact, equal. Analysis procedures involving post-stratification, and multiple regression will be used to adjust for any baseline group differences.

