Eligibility and Randomization Data Form	Clinical data: meets inclusion criteria and none of exclusion criteria; eligibility confirmed Research: date and time of randomization, and allocation of treatment arm (control vs intervention)	First 30 seconds of birth
Delivery Room (DR) Data Form	RESEARCH DATA collected: time infant is placed on resuscitation trolley; time of specific maneuver; 1 st sustained inflation and exact pressure measurement x 15 seconds; time of 2 nd sustained inflation and exact pressure measurement x 15 seconds; and use of ventilator vs T-piece	Research intervention takes place within the first 30 seconds up to 1 - 2 minutes of life
	Clinical data: time of birth, time of cord clamping, NRP guidelines used in the resuscitation of the infant such as respiratory status; blood gas values including glucose and hemoglobin/hematocrit values; procedures if any (intubation, chest compression, administration of epinephrine; surfactant delivery; UAC/UVC placement; chest tube placement and additional medications; final respiratory status before leaving DR; and outcome of resuscitation. Additional clinical information: date and time of birth, birth weight, Apgar score at 1 and 5 min, and gender	Certain clinical time points as dictated by the resuscitation process in the DR; data should be completed within first 48 hours

Data Collection Topic	Specific Data Elements	Specific time interval
Respiratory function measurements of inflations and physiologic monitoring (Obtained only at a subset of sites)	Inflation characteristics: pressure, flow, tidal volume, exhaled CO ₂ Physiologic monitoring: heart rate, oxygen saturation, delivered oxygen concentration	First 10 minutes of life
Delivery Room Video recording (obtained only at a subset of sites; transferred and destroyed after analysis)	Video recordings of the infant during the initial resuscitation and stabilization	Up to the first 30 minutes of life
Adverse Events	See Section 9.2 for detailed information.	Specific events during the first 10 days of life; thereafter continuing AE reporting structures are in place until the infant reaches 36 weeks GA
SNAPPE Score	Clinical data: severity score that is compiled by using clinical parameters within the first 12 hours of life, such as lowest pH, PaO ₂ and corresponding FiO ₂ and MAP, urine output and presence of seizures	Completed by first week of life

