5.1.1. Potential Confounders and Strategy to Limit Impact

Severity of initial illness: Randomization should achieve balance at baseline. Adjustment for SNAPPE scores on admission to the NICU will be performed during the analysis of the primary outcome.

Site Variation: Randomization will be stratified by site.

General respiratory management in the DR and beyond: Local unit protocols will be followed with respect to aspects of respiratory support not specifically addressed in the study interventions. In general, after initial resuscitation, CPAP will be the initial mode of respiratory support in reasonably vigorous infants. Intubation will be reserved for infants who remain apneic, are without adequate respiratory effort, or have persistent bradycardia. Surfactant for RDS prophylaxis will not be given in the DR prior to SI (if so randomized), even if the infant is intubated. Caffeine will be administered to infants if needed for respiratory support.

Extubation and intubation guidelines: Continued need for mechanical ventilation is associated with BPD. We adopt a uniform guideline to intubation and extubation, though clinical circumstances may preclude strict adherence to guidelines at all times. There is no consensus about weaning babies from mechanical ventilation. Therefore, the proposed extubation guidelines are based on consensus and criteria used in several current and recent large clinical trials. On a daily basis the infant will be assessed for ability to wean from ventilation. We will strongly encourage extubation to be attempted within 24 hours after meeting all following criteria: $PCO_2 \leq 55$ mm Hg and a $pH \geq 7.25$, FiO_2 of ≤ 0.4 with an SpO_2 of $\geq 88\%$ or higher, mean airway pressure of ≤ 8 cm of water, and hemodynamic stability and without evidence of clinically significant patent ductus arteriosus. All infants will have received caffeine prior to an extubation attempt. Extubation may be attempted at higher settings at the discretion of the clinical team. Following extubation all infants should be placed on nasal CPAP or NIPPV, not on nasal cannula or oxihood. In unplanned extubations, the infant will be given an opportunity to remain extubated, if heart rate and oxygen saturations are maintained without excessively high FiO_2 or work of breathing. Extubation will be considered successful if the infant remains extubated for at least 48 hours. Reintubation will be at the discretion of the clinical team managing the infant.

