6.1.2.2. Analysis of Primary Outcome

The primary endpoint to be used for efficacy evaluation is the rate of Death or BPD at 36 weeks gestation age. The primary hypothesis to be tested is that the treatment therapy results in a decreased event rate. Although a proportion's test is used for sample size calculations, rates will be compared using logistic regression, which will allow for control of covariates, as well as investigation of effect modification. Potential covariates include gender, gestational age, initial heart rate, maternal corticosteroids use, and small for gestational age (SGA). Clinical site will be used as a stratifying factor to control for any confounding by site through residual, site-level treatment imbalance. The logistic regression will be estimated using a generalized estimating equation (GEE) in order to adjust for the inherent correlation expected with multiples. Standard regression diagnostics will be used to assess model adequacy, and to examine for potential outlying or influential data points.

Prior studies offer no basis for assuming a priori interactions between treatment arms and subgroups defined by sex, race/ethnicity, gestational age, site or a combination of these groups, beyond that already controlled for in the randomization. For that reason, preplanned tests for interactions with treatment assignment are not warranted, and not powered for. We propose, however, to table all results by subgroups for descriptive purposes and to explore in secondary analyses possible subgroup differences by treatment group, solely for purposes of generating hypotheses for future studies. In particular, there is interest in exploring subgroups defined by:

- Consenting procedure which may vary by site (antenatal vs. deferred consent). While consenting procedure differences may result in some selection bias, this will be implicitly adjusted for with

the already planned clinical site stratification factor. Additionally, the sample size still results in 80% power at $\alpha=0.038$ for the primary outcome even if the selection bias results in a reduced control arm rate.

- Route of treatment (facemask vs. nasopharyngeal tube). While not expected to modify the intervention effectiveness, exploring this difference will be important for future study design and clinical practice.

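### SAP 5.4.1 leaves the final primary test unnamed and drops the protocol's site-stratified GEE model

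*SAP*

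**What the plan says.** **Protocol.** Section 6.1.2.2 says rates will be compared by logistic regression. It is firm on two features: "The logistic regression will be estimated using a generalized estimating equation (GEE) in order to adjust for the inherent correlation expected with multiples" and "Clinical site will be used as a stratifying factor to control for any confounding by site through residual, site-level treatment imbalance". Gestational age appears there only in a list of potential covariates. Section 4.4.4 gives the randomisation factors: "We have chosen to stratify the randomization scheme by clinical site, and gestational age", with strata of 23–24 and 25–26 weeks. The protocol makes two further promises about adjustment. Section 4.4.4: "We will perform a planned adjustment following the end of the trial to adjust for gender". Section 5.1.1: "Adjustment for SNAPPE scores on admission to the NICU will be performed during the analysis of the primary outcome".

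**SAP.** Section 1 says the plan covers the interim and final analyses that the protocol specifies. On the final primary analysis, section 5.4.1 says: "In addition to the two-sample comparison (Appendix B, Table 5), adjusted analyses of the primary endpoint (death/BPD rate) may be performed". Logistic regression and GEE are attached to those optional analyses. Their example covariates include gender and gestational age but neither site nor SNAPPE, and SNAPPE appears nowhere in the SAP. The consent-procedure bullet in the same section nevertheless relies on a site stratification factor described as already planned.

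The table cited, Appendix B Table 5, is the serious adverse event table. The primary endpoint is in Table 7, which shows a p-value placeholder and no method. Section 5.4.3 sets the final boundary at 0.038.

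**The concern.** One p-value decides the trial at the final look, and the documents do not say which model produces it. The SAP's only unconditional commitment is an unnamed comparison. The protocol's commitment is a site-stratified GEE. If the SAP is read as meaning a treatment-only GEE, it contradicts the protocol on site; if the protocol governs, the SAP text is wrong.

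The choice has consequences. Allocation is balanced within site and gestational-age stratum. When those factors affect risk, a test that ignores them uses a standard error that is too large, so it runs below its nominal level and gives up power. Different candidate models can also return different verdicts on the same data. Leaving that choice open in a trial with unblinded treatment is what pre-specification is meant to avoid.

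**Working it through.** **Do other sections settle the final test?**

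- SAP 4 specifies a GEE of death/BPD on treatment alone, for the interim looks.
- SAP 5.4.2 uses GEE for twins, for secondary endpoints.
- SAP 5.4.3 gives the boundary and SAP 6.3 the analysis set; neither gives a model.
- SAP 6.1 has a centre-adjusted method, for withdrawal rates.

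These make a clustered test the likeliest intent. None puts site into the final model.

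**Reproducing the plan's figure.** Inputs from Protocol 6.1.1: 65% versus 52.5%, α = 0.038, 80% power. SAP 5 makes tests two-sided. With the pooled-variance formula and mean rate 0.5875:

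n = {[2.075·√(2·0.5875·0.4125) + 0.842·√(0.65·0.35 + 0.525·0.475)] / 0.125}² = 262.6, so 263 per arm, as stated.

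Then 263 × 1.12 = 294.6, rounded up to 300. Reading 1.12 as a variance design effect, 300/1.12 = 267.9 effective infants per arm, with power 0.808.

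**Direction of each omission** (analytic, final look only):

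- Ignoring twin clustering: 2[1 − Φ(2.075/√1.12)] = 0.050.
- Ignoring strata that explain a share R² of outcome variance: 2[1 − Φ(2.075/√(1 − R²))] = 0.033 at R² = 0.05 and 0.029 at 0.10.
- Both together: 2[1 − Φ(2.075/√(1.12(1 − R²)))] = 0.044 and 0.039.

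The effects work in opposite directions, so an unclustered test has no fixed direction of error.

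**Simulation.** From the documents: about 600 infants, 21 sites, two gestational-age strata, 1:1 permuted blocks, multiples allocated together. Assumed, because the documents do not give them:

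- 528 deliveries, 13.6% twins, so 24% of infants are in twin pairs; within-pair correlation 0.5 (1 + 0.24 × 0.5 = 1.12)
- site sizes declining exponentially; blocks of 2 or 4
- 40% of infants at 23–24 weeks
- control risk centred on 65%, with stratum risks from 75% vs 58% to 85% vs 52%
- between-site SD 0.3–0.6 on the logit scale

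The GEE used an independence working correlation with cluster-robust variance. Sites under 15 infants were pooled and failed fits dropped. There were 10,000 runs per cell (Monte Carlo SE about 0.002 for levels, 0.4 points for power). Rejection was |z| > 2.075.

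Level under no effect:

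| Site SD; stratum risks | Unclustered | Treatment-only GEE | Site GEE | Site + stratum GEE |
|---|---|---|---|---|
| 0.3; 75/58 | .0466 | .0326 | .0346 | .0384 |
| 0.3; 80/55 | .0431 | .0316 | .0344 | .0384 |
| 0.6; 80/55 | .0383 | .0271 | .0313 | .0356 |
| 0.6; 85/52 | .0361 | .0250 | .0296 | .0408 |
| No site or stratum effect | .0512 | .0389 | .0398 | .0400 |

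Power at 65% vs 52.5%, and discordance with the treatment-only GEE (null / 12.5 points / 8.5 points):

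| Site SD; stratum risks | Power: treatment-only / site / site + stratum | Discordance: site | Discordance: site + stratum |
|---|---|---|---|
| 0.3; 75/58 | .811 / .817 / .830 | .0063 / .0147 / .0269 | .0095 / .0261 / .0417 |
| 0.3; 80/55 | .821 / .828 / .851 | .0054 / .0189 / .0282 | .0107 / .0385 / .0564 |
| 0.6; 80/55 | .809 / .831 / .850 | .0066 / .0321 / .0445 | .0114 / .0488 / .0738 |
| 0.6; 85/52 | .823 / .843 / .877 | .0077 / .0274 / .0418 | .0193 / .0575 / .0977 |
| No site or stratum effect | .810 / .812 / .812 | – | – |

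By subtraction in the first four rows, site gains 0.6 to 2.2 points of power over treatment only, and site plus stratum gains 1.9 to 5.4. With no site or stratum effect, adjustment costs nothing visible.

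**Analytic check on power.** Replacing 267.9 by 267.9/(1 − R²), with R² = 0.029, 0.066 and 0.117 for gestational age alone, gives 0.820, 0.835 and 0.856. That is in line with the simulated gains.

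**The case against.** The best case against is that this is missing detail, not a rival plan. In SAP 5.4.1 the optional wording governs covariate adjustment rather than the handling of multiples. SAP 4 calls adjustment for multiples necessary and sends the reader to the final-analysis section for further detail, so the unnamed comparison is naturally read as that same GEE. The SAP also mentions a planned site factor, and its covariate list is open-ended. On that reading clustering is handled, the test is conservative, and simulated power stays at 81–82%, above the planned 80%.

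Much of this stands. A clustered test is the likeliest intent, the unclustered reading is the least supported, and neither validity nor planned power is threatened. It does not close the gap: the treatment-only reading still departs from the protocol on site, and an optional, open-ended list does not define a confirmatory test.

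Three further objections are fair in part.

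- **The stratum.** The larger gains come from adding the gestational-age stratum, which neither document commits to. That is correct, and it is an improvement on the protocol rather than a restoration of it.
- **Failed fits.** Even after pooling, 0.1–3.5% of simulated trials had a failed fit, comparable to the treatment-only versus site discordance. A fallback must be stated in advance.
- **Mixed models across looks.** Only the final look was simulated, and the interim model is treatment-only. If each look holds its own level, the overall error cannot exceed 0.0002 + 0.012 + 0.038 = 0.0502, whichever models are used.

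**Conclusion.** The concern holds and should be fixed. SAP 5.4.1 does not define the test compared with 0.038 and omits the site stratification to which the protocol commits.

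The practical size is modest. For the main open choice, treatment-only versus site GEE, verdicts differ in 0.5–0.8% of trials under no effect, 1.5–3.2% at 12.5 points and 2.7–4.5% at a true 8.5 points. Against site plus stratum the figures are 1.0–1.9%, 2.6–5.8% and 4.2–9.8%. These ranges depend on the assumed twin share and correlation, stratum mix and risks, site variation and site sizes. The textual gap does not depend on them.

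The unreconciled SNAPPE and gender adjustments belong to the same defect. The table reference is clerical.

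**What to change.** In SAP 5.4.1:

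- **Name one primary test** for the 0.038 boundary: GEE logistic regression clustered on delivery, with treatment, site and gestational-age stratum (23–24 versus 25–26 weeks). Site restores Protocol 6.1.2.2. The stratum goes beyond it, but is the trial's other randomisation factor.
- **State in advance** how small sites are pooled and which model applies if the fit fails.
- **Keep GEE clustering** at the interim looks.
- **Make everything else supportive:** the unadjusted comparison, the gender adjustment and other covariate adjustments. SNAPPE also belongs here. The Study Data table in Protocol section 5 describes it as a "severity score that is compiled by using clinical parameters within the first 12 hours of life", so it is measured after the intervention and should not be in the primary test.
- **Cite Table 7** instead of Table 5.

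The cost is SAP wording and minor programming, since all the variables are already collected. The downside is that sparse sites have to be pooled.
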